Our *long-term goal* is to develop and implement dietary intervention(s) that reduce risk of T2D. The *overall goal of this randomized controlled trial is to study the effect of a behavioral intervention promoting a low-carbohydrate/high-unsaturated fat and high-protein dietary pattern (initial target <40 g digestible carbohydrates, final target <60 g digestible carbohydrates) compared with a usual diet on metabolic risk factors among individuals with prediabetes or early-stage untreated diabetes (HbA1c 6.0–6.9%).* Specifically, we will test the following hypotheses:

Primary hypothesis: Compared with usual diet, over a 6-month period, a healthy low-carbohydrate/high unsaturated fat and high-protein dietary pattern will lead to a larger decrease of HbA1c, by at least 0.15%.

Secondary hypothesis: Over a 6-month period, a healthy low-carbohydrate/high-unsaturated fat and high-protein dietary pattern will lead to larger improvements in the following major secondary outcomes: fasting glucose, systolic blood pressure (BP), total-to-HDL-cholesterol ratio, and body weight.

Exploratory outcomes: We will also study the effect of the intervention on the 6-month change in: insulin and homeostasis model assessment of insulin resistance (HOMA-IR); diastolic BP; waist circumference; and estimated CVD risk.

To achieve these study aims, we will recruit 150 adults with prediabetes or untreated diabetes (HbA1c 6.0–6.9%) in the Greater New Orleans, LA area. Using a stratified, blocked randomization scheme, participants will be assigned to either a behavioral modification intervention aimed at promoting a healthy low-carbohydrate dietary pattern or to usual diet. The intervention group will have an intensive phase for 3 months, followed by a maintenance phase in months 4 through 6. The primary outcome will be difference between the active intervention and control groups in the change in HbA1c from baseline to 6 months of follow-up. We expect 80% power to detect a difference of at least 0.15% in change of HbA1c. Changes in other metabolic risk factors will be studied concurrently. Metabolic risk factors will be assessed at baseline, 3 months, and 6 months of follow-up.

There is much interest regarding dietary approaches to prevent T2D and its complications. The results from this study will help to determine whether, compared with usual diet, a behavioral intervention aimed at promoting a healthy low-carbohydrate dietary pattern improves metabolic risk factors.

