Strategies for measuring compliance: For the low-carbohydrate diet, adherence will be assessed through measurement of urinary ketones at 3-month visit and 6-month TV. Study staff will make all reasonable effort to maintain adherence of participants to the visit schedule and diet intervention.

Strategies for improving compliance:

- At the screening visit, we will ask participants who does most of the cooking in their households and how often they eat outside of the home. Results from the screening visit will help to select a group of cooperative study participants.
- Visits will be scheduled at the participants' convenience and to minimize waiting time and trips to the clinic; reminder calls, texts or emails (chosen based on participant preference) will also be made prior to clinic visits.
- We will hire enthusiastic staff who have good interpersonal skills.
- Participants will receive \$40 gift cards for use at food stores or retailers when they complete each study visit, for a maximum of \$120 over the study period.
- Participants will receive \$25 gift cards when they return the stool specimens, for a maximum of \$75 over the study period.

- Participants will receive a \$25 gift card when they return the continuous glucose monitor, for a maximum of \$25 over the study period.
- Participants will be offered small gifts (such as pens or magnets with study logo) to encourage compliance and adherence to the study protocol.
- Participants will be provided with recipes, shopping lists, and food samples for the intervention diet.

9. Safety of Dietary Intervention

On the low-carbohydrate diet, participants will be encouraged to primarily focus on replacing carbohydrates (particularly highly refined carbohydrates) with foods such as non-starchy vegetables, olive oil and other plant-based unsaturated oils, nuts and seeds, avocados, eggs, seafood, tofu, poultry, and lean meat. Consumption of more unsaturated fats, protein, and fiber will be recommended. Participants will not be encouraged to increase consumption of saturated fats and will be advised to avoid consumption of trans fats.

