In animal studies, a high-protein diet has decreased renal function¹⁰⁵ In the MACRO study, on average, participants tended to increase consumption of fats, rather than protein.³⁰ The safety and tolerability of low-carbohydrate diets have previously been assessed in many studies, including MACRO.³⁰ A number of studies, including some in individuals with T2D, have found no clinically significant increases in estimated glomerular filtration rates,^{33,38–40} microalbuminuria,¹⁰⁶ albumin excretion rate,^{33,38} urinary albumin,³⁸ serum creatinine,^{38,40,106–111} albumin,⁴⁰ or uric acid levels.^{107–110} A small study of a very low-carbohydrate diet found significant increase in uric acid excretion, but no significant change in 24-hour urine creatinine clearance.¹¹⁰

Study staff will carefully monitor participants' BP, and HbA1c more often than what would occur in routine healthcare visits. A Data Safety and Monitoring Board (DSMB) consisting of an independent group of experts in areas such as biostatistics, nutrition medicine, general internal medicine, and endocrinology has been formed. The board will regularly review trial progress, including unblinded interim results, and can recommend that the trial prematurely end if participants are at risk or if it becomes clear that the trial will not be able to yield statistically significant results.

10. Data Collection

10.A. Study visits

After the initial pre-screening interview, in which data on medications and medical conditions will be collected, there will be one screening visit, one randomization visit, a follow-up study visit at 3 months and a termination visit (TV) at 6 months. **Table 3** summarizes study procedures and data collected at each study visit.

Table 3. Study visit schedule and data collection

	Pre-screen	SV	RZ	3 month	6 month TV
Pre-screen eligibility	X				
Informed consent		X			
Compliance form		X			
Eligibility confirmation			X		
Randomization			X		
Demographics		X			
Medical history questionnaire			X	X	X
Medications	X	X	X	X	X
Lifestyle (alcohol, cigarette smoking)		X	X	X	X
Physical activity		X	X	X	X
24-hour diet recall*		X	X	X	X
3 BP measurements	X	X	X	X	X
Body weight		X	X	X	X
Height		X			
Waist circumference		X	X	X	X
Spot urine test		X	X	X	X
Blood samples	X	X	X	X	X
Stool specimen		X	X	X	X
Side-effects assessment		X	X	X	X
Nut Consumption					X
CGM**					X

*Two 24-hour dietary recalls will be collected; one should cover a weekend and the other a weekday.

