**The CGM will be worn for up to 14 days prior to the 6-month TV and returned at the TV or by mail. Participants will come in for a 6-month CGM visit (prior to the 6-month TV) to have the CGM inserted.

10.A.1. Screening/baseline visits:

Participants will be pre-screened by phone or in-person by study staff to confirm eligibility for the Screening Visit. An approved questionnaire will be used to ensure the patient is eligible to attend the in-clinic screening visit, and the patient will be scheduled thereafter.

At the screening visit (SV), participants will provide informed consent for the screening and main study. Study staff will schedule the SV and randomization (RZ) visit at least 2 days apart. If a participant is eligible based on the screening visit, he or she should be scheduled for the RZ once a sufficient group of eligible individuals has been recruited. Participants should be scheduled for the RZ at least 2 days and no more than two weeks after the screening visit.

At the screening visit, we will collect information on inclusion/exclusion criteria, medication use, and demographics. At this visit, we will also have participants complete a compliance form,

to assess their ability to complete the study and attend all intervention and study visits. We will also measure blood pressure, and take blood samples. Women will be asked if they are postmenopausal or if they had surgical sterilization (such as a tubal ligation). If not, they will be tested for pregnancy through a spot urine test; pregnant women will be excluded from the study. Blood samples will be collected for measurement of HbA1c, and, if not available from medical records in the past 3 months, serum creatinine and hemoglobin. These blood samples will be used for excluding individuals with HbA1c <6.0 or >6.9, eGFR ≤45 mL/min/1.73 m², or hemoglobin <11 mg/dL.

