10.B.3. Assessment and management of adverse effects: At RZ, 3-month visit, and 6-month TV, we will administer *symptom questionnaires*, which will consist of a checklist to identify participant complaints. Prior studies of low-carbohydrate dietary interventions suggest that participants may experience a range of adverse effects, including constipation, halitosis, fatigue, headache, thirst, polyuria, and nausea. Severe adverse events will be promptly reported to the DSMB. Management of adverse effects will be based on the protection and safety of the participant. If severe adverse effects are reported by a participant, carbohydrate intake will be examined and altered in order to mitigate the adverse effect. In any extreme cases, participants will be instructed to stop the intervention. As this is a behavioral intervention, adverse effects should be rare.

10.B.4. BP and anthropometric measures: BP will be measured 3 times at the screening visit and at each follow-up visit. To minimize random error, averages of the measurements at the screening and randomization visits will be taken. BP will be measured by a standard automated blood pressure measurement device (OMRON HEM-907 XL Professional Digital Blood Pressure Monitor) and performed by experienced staff, trained and certified in BP measurement. Prior to BP measurements, participants will be asked to rest quietly in a seated position with their feet supported for at least 5 minutes; staff members will use an appropriate cuff size over a bare arm. Trained and certified staff will measure weight using a calibrated balance beam scale at the screening visits, and follow-up visits. Weight and height will be measured at the RZ, and weight will also be measured at the subsequent visits.

10.B.5. Blood samples: For SV, participants will not need to fast. For RZ, 3-month visit, and 6-month TV, participants will be instructed to fast for 12 hours prior to blood sample collection. At SV, blood samples will be collected to measure HbA1c, hemoglobin, and serum creatinine. At RZ, fasting blood samples will be collected and stored as serum/plasma, whole blood aliquots and buffy coats at -80°C for future analyses, including measurement of glucose, insulin and lipids, and potential future metabolomics or genetic analyses. At 3-month visit and 6-month TV,

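### No kidney-function measure is scheduled after screening, so a silent decline on the diet would not be seen while the trial runs and no renal comparison between arms is planned

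*Combined protocol and SAP*

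**What the plan says.** **The concern and the plan's answer (section 9).** The safety section notes: "In animal studies, a high-protein diet has decreased renal function". It gives two replies. In the group's earlier low-carbohydrate trial, "participants tended to increase consumption of fats, rather than protein". And: "A number of studies, including some in individuals with T2D, have found no clinically significant increases in estimated glomerular filtration rates"; the same sentence goes on to albuminuria measures, serum creatinine and uric acid.

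**The diet.** The primary hypothesis in section 1 begins: "Compared with usual diet, over a 6-month period, a healthy low-carbohydrate/high unsaturated fat and high-protein dietary pattern". Section 9 adds: "Consumption of more unsaturated fats, protein, and fiber will be recommended". No protein target is given.

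**Eligibility (section 6.A).** An eGFR of 45 or lower excludes, and it is grouped with medical conditions in which a low-carbohydrate diet may be inadvisable.

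**When creatinine is measured.** Section 10.B.5: "At SV, blood samples will be collected to measure HbA1c, hemoglobin, and serum creatinine". Table 4 gives creatinine a single mark. Section 10.A.1 has it drawn only "if not available from medical records in the past 3 months, serum creatinine and hemoglobin", and its stated use is exclusion. Section 16.A.1 (Sources of materials) lists creatinine among the blood and urine tests and names no visit.

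**Monitoring during follow-up.** Section 9 says that staff will watch "BP, and HbA1c more often than what would occur in routine healthcare visits". Serum and plasma are frozen at RZ, 3 and 6 months for glucose, insulin, lipids and unspecified later assays. Spot urine is taken for ketones and unspecified markers (10.A.2, Table 4).

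**The concern.** The plan uses kidney function to decide who may enter, discusses it in the safety section, and then does not measure it again. The two quantities that section 9 offers for closer monitoring, blood pressure and HbA1c, do not measure kidney function. A participant could enter just above the eGFR exclusion, fall below it on the diet without symptoms, and not be picked up by any scheduled test.

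Two safeguards already in the plan depend on current results: the referral of participants with clinically abnormal laboratory values (16.A.3) and the DSMB's twice-yearly review of cumulative safety data (16.B). Without a creatinine result, neither can respond to a silent change. At the end, the trial would also have no planned renal safety comparison to report, although section 9 raises the question itself.

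The primary and secondary efficacy estimates are not affected. This is about participant safety and what the trial can say about it.

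**Working it through.** The plan states no figure on this point, so the check compares the schedules and counts what they yield.

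| Time point | Blood drawn? | Creatinine scheduled? | Source |
|---|---|---|---|
| Screening | Yes | Yes, or a record value up to 3 months old | 10.A.1, 10.B.5, Table 4 |
| RZ | Yes, fasting, stored | No | 10.B.5, Table 4 |
| 3 months | Yes, fasting; fresh HbA1c plus storage | No | 10.B.5, Table 4 |
| 6 months | Yes, fasting; fresh HbA1c plus storage | No | 10.B.5, Table 4 |

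1. **Values per participant.** There is at most one study-measured creatinine, and possibly none where a record value is accepted. A within-person change needs two values, so the scheduled tests give no estimate of eGFR change in either arm.

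2. **Unused opportunity.** Post-randomization fasting draws: 2 × 150 = 300. With RZ: 3 × 150 = 450. These are maxima, before loss to follow-up.

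3. **Participants who move.** For blood taken at an outside laboratory, section 10.B.5 names HbA1c, glucose, insulin and lipids. Creatinine is absent here too.

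4. **Analysis.** Neither the outcomes in 4.B, nor Table 5, nor the analysis plan in 13.B contains creatinine or eGFR.

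5. **What measurement would allow.** Table 5 and section 12 assume 95% follow-up, and 0.95 × 75 = 71.25, so about 71 in the diet arm. If none of 71 had a decline meeting some pre-stated definition, the one-sided 95% upper limit for the rate would be 1 − 0.05^(1/71) = 1 − 0.959 = 0.041, or 4.1%. This is the generic zero-event limit for 71 people. It shows what could be learned and is not an estimate of harm. The documents do not define such a decline.

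6. **What cannot be computed.** The documents give no SD, expected change or baseline distribution for eGFR. No detectable difference, and no count of participants entering near the exclusion limit, can be derived.

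7. **The reassurance set against this trial.** The earlier trial enrolled people without diabetes (3.B), and its participants raised fat rather than protein. This trial recommends more protein and enrolls untreated HbA1c up to 6.9%. For eGFR, the cited studies are said to show no important increases, whereas the concern is a decrease. That may only be the verb fitting the other items in the list, for which an increase is the adverse direction.

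**The case against.** The other side has several fair points.

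- **The plan argues the risk is low.** Section 9 reports an animal finding and answers it with several human studies, some in type 2 diabetes. Potential Risks in 16.A.1 omits renal function. A reader might infer that the protocol declares renal decline a known risk of this diet; it does not. What stands is that section 9 raises the question and 6.A acts on it at entry.
- **Blood is kept.** A reader might infer that a decline could never be detected, or that no rate could ever be bounded. The stored RZ, 3- and 6-month serum in both arms rules that out: creatinine could be assayed later, giving change by arm and the same 4.1% limit. What stands is that no such assay is planned and that late results cannot help a participant during the trial.
- **Other routes exist.** Medical history and symptom questionnaires at RZ, 3 and 6 months (10.B.1, 10.B.3), adverse-effect checks at counseling, and reporting of severe events to the DSMB could bring diagnosed or symptomatic kidney disease to light. It would be wrong to say that affected participants are never identified. These routes would still miss a silent fall.
- **The contrast with the earlier trial is limited.** Materials are adapted from it, counseling stresses unsaturated fat, and no protein target is set (8.A). Protein intake may rise little. This lowers the expected risk but leaves it unmeasured.
- **The kidney is not the only exclusion without follow-up tests.** Liver disease, osteoporosis, thyroid disease and gout sit beside it in 6.A. But those rest on self-report, while eGFR is the one condition in that group defined by a laboratory value, and section 9 discusses kidney function at length.

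**Conclusion.** The point holds as a gap in safety measurement. Creatinine is scheduled at screening only, or taken from a recent record. No renal measure is named after randomization, and no renal comparison is planned. A silent decline would go unseen in real time.

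Its size is zero scheduled post-randomization values where up to 300 samples will be in hand. Nothing in the documents shows that harm is likely, and the human studies cited in section 9 point to a low prior risk. The conclusion rests on reading 10.B.5 and Table 4 as the governing schedule. The undated mention of creatinine in 16.A.1, and the unspecified later assays and urine markers, leave open that more was intended. If so, the plan should say it.

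This is a worthwhile, inexpensive improvement and not a flaw that threatens the trial's main result.

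**What to change.** 1. In Table 4 and section 10.B.5, add serum creatinine with eGFR at RZ, 3 months and 6 months in both arms, on the fasting blood already drawn. Run it fresh, by the same laboratory and method throughout, with RZ as the common baseline. Add it also to the tests for participants who move.
2. Where RZ blood is already frozen, assay the stored RZ, 3- and 6-month serum together for the between-arm comparison. Fresh 3- and 6-month results are still needed for safety.
3. In 13.B, state that eGFR change by arm will be estimated with a confidence interval, as a safety analysis. Include it in the DSMB tables under the masked-group arrangement in 16.B.
4. Send abnormal values through the referral already promised in 16.A.3. No new clinical threshold or diet rule is proposed here.
5. Reconcile section 9, 10.B.5 with Table 4, and 16.A.1, so that each agrees on when creatinine is measured and whether renal function is treated as a potential risk.

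**Cost.** Up to 3 × 150 = 450 routine tests and an edit to the schedule, with no new visit or venipuncture. Fresh HbA1c is already run at 3 and 6 months, so the sample route exists there; a fresh test at RZ would be new. The downside is a modest laboratory cost and some abnormal results to handle.
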